2. What are the sociodemographic and clinical characteristics of patients that may influence results regarding measurement of clinical and organizational quality indicators of acute stroke care?

Research hypotheses

1. Results highlight gaps between guidelines and practice following measurement of clinical and organizational quality indicators during acute management of patients with ischemic stroke.
2. Gaps between guidelines and practice resulting from measurement of the clinical and organizational quality indicators of acute stroke care may present similarities or differences between types of hospital centers.
3. Some of patients' clinical and sociodemographic characteristics influence the achievement of the clinical and organizational quality indicators of acute stroke care.
4. Patients' sociodemographic and clinical characteristics identified as influencing the achievement of clinical and organizational quality indicators may vary depending on types of centers.

3. Methodology

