3.1 Type of study

To meet the objectives of the research questions, a retrospective descriptive-correlational study will be conducted based on methods of collecting and analyzing quantitative data. The decision to conduct a retrospective study was made for two reasons: first, the nature of the data collected from records allows us to describe the current state of clinical and organizational practices during the length of patients' stay; and second, this type of study

May 2022

page 11 de 48

[name], [name], [name]

allows for the inclusion of a sample of patients hospitalized during a fixed six-month period. Finally, the feasibility of a retrospective study was considered within the context of a doctoral project with limited resources, time and budget.

In keeping with these considerations, the present study involves a multicentric investigation to take place in three differently designated Quebec hospitals in terms of stroke care. The choice of a multicentric study is based on using a larger sample of patients from different areas to obtain a broad overall view of clinical and organizational practice in stroke management in Quebec. In this study, the primary care center is a multi-vocational center including hospital care that is located in a remote area. The second participating center is a secondary care university hospital that plays an important role in the optimization of stroke care and services throughout its territory given its status as a regional center. The third hospital targeted by the study is a specialized tertiary care center which is nationally recognized for stroke treatment and performs the most thrombectomies in Quebec.

Having different and welldefined missions, these centers maintain an interdependent relation through the offer of proposed care and services. Notably, the patients from the primary care center requiring a thrombectomy are generally transferred to the tertiary center participating in this study to receive treatment. Additionally, although the tertiary care hospital is a thrombectomy center, the patients transferred there must also be returned to the secondary care referral center quickly after treatment to begin rehabilitation as early as possible. Since the majority of guidelines apply in all types of centers irrespective of where the patient is managed, each center must self-compare regarding the achievement of quality indicators.

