8.1 Strengths

This first study on the measurement of acute stroke quality indicators in Quebec allows for an evaluation of performance of care and services based on various clinical and organizational aspects. Indeed, the study's main strength is the measurement of diverse dimensions of performance of care that enables a picture of interdisciplinary practice for the entire acute phase of ischemic stroke. The implementation of the study in three different Quebec hospitals will also provide a better understanding of their distinct geographic and structural contexts. Inclusion of health records from three different centers also allows for better representativity of the population with stroke. As well, the rigorous method employed during implementation can be used by other organizations to obtain results specific to their own establishment. Finally, this retrospective study including a data collection close in time will enable an accurate picture of clinical and organizational management within the context of current healthcare.

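### Hypotheses 2 and 4 are about types of hospital, but with one hospital per designation the study can only speak about the three participating hospitals.

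*Protocol*

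**What the plan says.** Section 2 of the protocol lists four research hypotheses, two of which are framed by type of hospital. Hypothesis 2 says that gaps between guidelines and practice "may present similarities or differences between types of hospital centers". Hypothesis 4 says that the patient characteristics found to matter "may vary depending on types of centers".

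Section 3.1 describes a "multicentric investigation to take place in three differently designated Quebec hospitals in terms of stroke care", one hospital per designation. It gives each hospital features beyond its designation:

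- **Primary:** "the primary care center is a multi-vocational center including hospital care that is located in a remote area".
- **Secondary:** "The second participating center is a secondary care university hospital", which also serves as a regional centre.
- **Tertiary:** "nationally recognized for stroke treatment and performs the most thrombectomies in Quebec".

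Section 3.3.2 expects about 75 tertiary, 45 secondary and 8 to 10 primary records. Section 3.5 describes the indicators for each centre and for all three together. Regressions are run on the pooled records and may also be shown separately for the secondary and the tertiary centre. There is no separate regression for the primary centre.

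The limitations in section 8.2 cover separate databases, missing data, quality of notes, input errors, the choice of priority indicators, hospital characteristics that must be gathered by consultation, and the fact that associations with determinants do not show cause. That hospital and designation cannot be told apart is not among them.

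**The concern.** A statement about types of hospital needs some measure of how much hospitals of the same type differ from one another. With one hospital per type there is none. If the secondary and tertiary hospitals differ on dysphagia screening, for example, the cause may be designation. It may equally be one hospital's staffing, local protocols, record system or habits of note-keeping. Section 3.1 makes this concrete, since remoteness, university status and an exceptional thrombectomy volume each coincide with one designation. Section 8.2 adds that the databases differ between hospitals and that results depend on the quality of the notes.

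At stake is how the results are read. A conclusion in the words of hypotheses 2 and 4 would tell other primary, secondary or tertiary hospitals something that the data cannot show.

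**Working it through.** **Inputs.** Hospitals: 3; designations: 3 (section 3.1). Records: 75 + 45 + 8 = 128 to 75 + 45 + 10 = 130, which agrees with the stated figure of about 130 (section 3.3.2). Annual admissions: 400 + 250 + 12 = 662, which agrees with the stated figure of about 660; half a year is 662 / 2 = 331.

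**Step 1: degrees of freedom between hospitals.** Hospitals have 3 − 1 = 2 degrees of freedom in total. Types have 3 − 1 = 2. Hospitals within type have 3 − 3 = 0. A contrast between types can be computed, but it is identical to the contrast between hospitals, and nothing is left with which to judge ordinary variation between hospitals of one type.

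**Step 2: can a model separate the two?** A model with one indicator column per type (three columns) for 130 records has rank 3. Adding one indicator column per hospital (three more) leaves the rank at 3. Each hospital column duplicates a type column, so the two effects are fully aliased.

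**Step 3: would more records help?**

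| Records | Total df | Type (= hospital) | Hospitals within type | Records within hospital |
|---|---|---|---|---|
| 130 | 129 | 2 | 0 | 127 |
| 331 (all six-month admissions) | 330 | 2 | 0 | 328 |

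Extra records enlarge only the last column. The power statement in section 3.3.2 does not bear on this either, because it counts records and not hospitals. At least two hospitals in some designation would be needed before variation within type could be estimated at all.

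**Step 4: what is actually analysed for each hypothesis?**

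| Hypothesis | Unit named | Analysis in section 3.5 | What it can support |
|---|---|---|---|
| 2 | Types of hospital | Description by centre and overall | Differences among three hospitals |
| 4 | Types of centre | Optional separate regressions, secondary and tertiary | Differences between two hospitals |

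Hypothesis 4 is therefore too wide in two ways: it speaks of types rather than hospitals, and it takes in the primary designation, for which no separate analysis is planned.

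**The case against.** The strongest reply is that the protocol never sets out to attribute anything to designation. The study is called descriptive-correlational, both hypotheses say only that things may differ, and section 3.5 contains no test between types and is already worded by centre. Section 3.1 says that each centre must compare itself with itself. Section 3.4.3 and Appendix 3 collect staffing, ratios, experience, protocols and resources for each hospital, so that results can be read in context. On this view, type is shorthand for the three differently designated sites.

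Most of this stands, and it limits the point to wording and interpretation. It does not remove it. The hypotheses still name type as the unit of inference. The instruction on self-comparison argues for rewording them rather than for leaving them. The contextual description helps in discussing a difference but cannot break the aliasing with one hospital per type. The sentence in section 8.2 on cause concerns patient determinants, not designation.

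A reader might infer more than the documents support:

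- **That a planned test is invalid, or that type has no degrees of freedom.** Section 3.5 specifies no such test. Type has 2 degrees of freedom; it is hospitals within type that have 0.
- **That no difference at all can be linked to designation.** This is too absolute. Some differences follow from how the designations are defined in the introduction, and Appendix 1 marks Indicators 3 and 7 as not applicable in a primary centre.
- **That the error can be given a size in percentage points.** That would need an intraclass correlation between hospitals, which the documents do not give, for a between-type contrast that they do not plan.
- **That section 8.1 must withdraw its statement on representativity.** It says "Inclusion of health records from three different centers also allows for better representativity of the population with stroke", which is a comparative statement, and the synopsis limits the sampling claim to patients hospitalized in the three hospitals.

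**Conclusion.** The point holds as one about scope. Two of the four hypotheses name a unit of inference, the type of hospital, that the design cannot reach. Hospitals within type have 0 degrees of freedom, and this stays so at any number of records. The conclusion rests only on there being one hospital per designation, which section 3.1 states, and needs no assumed figure.

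No sampling, data collection or planned analysis is invalidated. Describing the three hospitals separately and together remains sound, as does a cautious comparison of the secondary with the tertiary hospital. A conclusion worded as hypotheses 2 and 4 are now worded would not be supported, and section 8.2 does not warn the reader of this.

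**What to change.** 1. In hypothesis 2, replace the reference to types of hospital centre with *the three participating hospitals*.
2. In hypothesis 4, replace the reference to types of centre with *the secondary and tertiary participating hospitals*, the only ones for which separate regressions are foreseen.
3. Word the conclusions in the same way.
4. Add to section 8.2 that each designation is represented by one hospital, so that a difference between hospitals cannot be separated from a difference between designations.

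The cost is a few sentences and a narrower claim. Sample, data collection and analyses are unchanged.

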3.1 Type of study

To meet the objectives of the research questions, a retrospective descriptive-correlational study will be conducted based on methods of collecting and analyzing quantitative data. The decision to conduct a retrospective study was made for two reasons: first, the nature of the data collected from records allows us to describe the current state of clinical and organizational practices during the length of patients' stay; and second, this type of study

May 2022

page 11 de 48

[name], [name], [name]

allows for the inclusion of a sample of patients hospitalized during a fixed six-month period. Finally, the feasibility of a retrospective study was considered within the context of a doctoral project with limited resources, time and budget.

In keeping with these considerations, the present study involves a multicentric investigation to take place in three differently designated Quebec hospitals in terms of stroke care. The choice of a multicentric study is based on using a larger sample of patients from different areas to obtain a broad overall view of clinical and organizational practice in stroke management in Quebec. In this study, the primary care center is a multi-vocational center including hospital care that is located in a remote area. The second participating center is a secondary care university hospital that plays an important role in the optimization of stroke care and services throughout its territory given its status as a regional center. The third hospital targeted by the study is a specialized tertiary care center which is nationally recognized for stroke treatment and performs the most thrombectomies in Quebec.

Having different and welldefined missions, these centers maintain an interdependent relation through the offer of proposed care and services. Notably, the patients from the primary care center requiring a thrombectomy are generally transferred to the tertiary center participating in this study to receive treatment. Additionally, although the tertiary care hospital is a thrombectomy center, the patients transferred there must also be returned to the secondary care referral center quickly after treatment to begin rehabilitation as early as possible. Since the majority of guidelines apply in all types of centers irrespective of where the patient is managed, each center must self-compare regarding the achievement of quality indicators.

3.2 Target population

The target population consists of adults 18 years old and over with ischemic stroke who are hospitalized in an acute care unit or a specialized stroke care unit. The only exclusion criterion is a hemorrhagic stroke.

3.3 Sample

3.3.1 Sampling methods

A random sample composed of the health records of patients hospitalized during a fixed period who meet inclusion and exclusion criteria will be included in the study. The list of randomly selected records of patients admitted to hospital for ischemic stroke in each of the participating centers during the six months prior to the date of approval by the Research Ethics Board (REB) will be transmitted by the archives service to the principal investigator. Data collection based on health records relative to clinical and organizational quality indicators will be performed by the principal investigator and a research assistant if needed. Additionally, the principal

investigator will collect data on the characteristics of each hospital center by consulting the health professionals and managers available at the time of observation and data collection.

3.3.2 Sample size

Calculation of number of records aims for a certain representativity of the target population at the time of data collection. Given that about 660 patients are hospitalized each year with ischemic stroke in the three centers under study - 400 in the tertiary center, 250 in the secondary center and 12 in the primary center - and the data were collected over a period of 6 months, the sample size is estimated to be some 130 health records, i.e., about 75, 45 and 8 to 10 records respectively. A power calculation in G*Power on analyses of group averages indicates this sample size is largely sufficient to have a power of 95 %, an alpha set at 0.05 and a minimal size effect of 0.5. When the size effect is not known, a minimal size effect of 50 % is acceptable (Julien, 2019). However, a first phase test will be performed with the health records of patients (n =6) hospitalized prior to the date set for the start of data collection to evaluate the average time required to analyze a record. This phase test will be performed on three health records from the secondary center and three from the tertiary center. Finally, this phase will enable needed adjustments to be made regarding implementation of research within the context of a doctoral study. Additionally, the principal investigator will have access to resources to validate the statistical analysis plan for the study duration.

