Target hospitals	1) Primary care hospital for stroke management 2) Secondary care hospital for stroke management 3) Tertiary care hospital for stroke management
Objectives and research questions	
Objective 1: Describe performance of care and services based on measurement of clinical and organizational quality indicators of acute stroke care in differently designated Quebec hospitals (primary, secondary and tertiary).
 
Research question 1: What is performance of care and services based on measurement of clinical and organizational quality indicators of acute stroke care in differently designated Quebec hospitals (primary, secondary and tertiary)?
 
Objective 2: Identify the sociodemographic and clinical characteristics of patients that may influence results regarding measurement of clinical and organizational quality indicators of acute stroke care.
 
Research question 2: What are the sociodemographic and clinical characteristics of patients that may influence results regarding measurement of clinical and organizational quality indicators of acute stroke care?

Target population	
Adults with ischemic stroke
 
All persons hospitalized for ischemic stroke within the 6 months preceding approval of the Research Ethics Board (REB). The study will be conducted based on their health records.

Inclusion criteria	Adults 18 years old or over with ischemic stroke requiring hospitalization in an acute care unit or special stroke unit
Exclusion criteria	Adults with hemorrhagic stroke
Type of study	Retrospective descriptive-correlational study
Period covered by study	6-month period preceding approval of the REB
Sample size	
Given that about 660 patients are hospitalized for ischemic stroke each year in the three hospitals under study and the data will be collected over a period of 6 months, sample size is estimated to be about 130 health records.
 
Because the minimal effect size is not known, an effect size of 50 % is used. A power calculation in G*Power on analyses of group averages indicates

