	
this sample size is largely sufficient to have a power of 95 %, an alpha set at 0.05 and a minimal effect size of 0.5. The number of patient records retained will provide a sample representative of the hospitalized population in the three hospitals.
 
Finally, a records evaluation test (n=6) will be performed in advance to estimate the time needed to examine each record and allow needed adjustments to be made to conduct research within the context of a doctoral study.

Data collection	
Results measurement:
 
 • Retrospective data collection performed on patients' health records included in the study (patients' sociodemographic and clinical data, results of evaluation of clinical and organizational quality indicators) • Description of hospitals through data collected on their characteristics based on an analysis of the environment and context of the different centers. This data collection will be performed using a structured interview guide (targeted questions) to identify hospitals' characteristics according to the clinical documentation and consultations with various clinicians, managers and doctors available in the centers under study.
Data analysis	
Statistical analyses will be conducted using SPSS software to meet the study's objectives.
 
Objective 1: Retrospective descriptive analysis based on patients' health records
 
Objective 2: Univariate and multivariate analyses; type of analysis based on type of variable (linear and logistical) and according to distribution (parametric and nonparametric tests)

Anticipated impacts	
 • Broaden the state of knowledge regarding acute ischemic stroke by drawing a picture of stroke patient management in three differently designated Quebec hospitals; • Identify the sociodemographic and clinical determinants that may influence the results of certain indicators; • In the long term, this project may contribute to reduce the gap between current practices and guidelines regarding post-acute stroke management; • Optimize acute stroke care and services across Quebec through improved understanding of different hospital contexts.

1. Introduction

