3.4 Tools and data collection

Data collection will begin once ethical approval is given (REB) and will be conducted using the health records of patients hospitalized during the 6 months preceding this approval. Archivists in each center in the study will provide randomly selected lists of the health records of patients meeting inclusion criteria. Data collected on each of the variables under study will be stored in a password-secured file. The complete list of clinical and organizational quality indicators in the scoping review is presented in Appendix 1. The data collection sheet on patients' characteristics and clinical and organizational quality indicators is given in Appendix 2.

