This study will be carried out retrospectively by analyzing the health records of patients meeting the admissions criteria. This type of study is more in line with a practice assessment process where the patient's consent is not considered necessary according to the 2018 Tri-Council Policy Statement (TCPS2). However, authorization by the Direction des services professionnels et de la pertinence clinique (DSPPC) following ethical approval of the research is needed to access patients' health records.

5. Project progress

After the ethics certificate and a letter authorizing access to health records have been obtained from the Direction des services professionnels et de la pertinence clinique (DSPPC), the random list of 130 health records of patients admitted within the preceding 6 months can be transmitted to the principal investigator to initiate data collection. Random lists of health records meeting the criteria will be drawn up by an archivist in each of the centers. The data will be collected in all three hospital centers at once based on availability of records.

6. Ethical and regulatory considerations

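### Section 3.3.2 plans 8 to 10 randomly selected primary-centre records from a six-month window that, on its own volumes, should hold about 6 (minor)

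*Protocol*

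**What the plan says.** Section 3.3.2 gives yearly ischemic stroke volumes of "400 in the tertiary center, 250 in the secondary center and 12 in the primary center", takes a six-month collection period, and then states that "the sample size is estimated to be some 130 health records, i.e., about 75, 45 and 8 to 10 records respectively". The order is tertiary, secondary, primary.

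Three other places describe how the records are obtained, and none exempts the primary centre:

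- Section 3.3.1: "The list of randomly selected records of patients admitted to hospital for ischemic stroke in each of the participating centers during the six months" before ethics approval is sent to the principal investigator.
- Section 3.4: "Archivists in each center in the study will provide randomly selected lists of the health records".
- Section 5 (Project progress) refers to "the random list of 130 health records of patients admitted within the preceding 6 months".

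Section 3.5 plans descriptive results for each centre and for the three together. Regression results are to be given for the three centres pooled, and possibly for the secondary and tertiary centres separately. No separate regression is planned for the primary centre.

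**The concern.** The yearly volume, the window and the planned count stand in one sentence, and for the primary centre they do not fit together. A random sample has to be smaller than the pool it is drawn from. Here the planned count exceeds the expected pool.

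Two things are at stake. First, the primary centre is one of the three hospital types that Objective 1 sets out to describe, and its proportions would rest on fewer records than the plan announces. Second, an archivist asked for a random list of 8 to 10 records has no stated rule for a window that holds about 6. The eventual report would also describe as a random sample what was in fact every available record.

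**Working it through.** **Inputs, all from section 3.3.2.** Yearly volumes: 400 tertiary, 250 secondary, 12 primary. Window: 6 months. Planned records: 75, 45 and 8 to 10.

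**The plan's own totals.** Volumes: 400 + 250 + 12 = 662, which agrees with the stated figure of about 660. Planned records: 75 + 45 + 8 = 128 and 75 + 45 + 10 = 130, which agrees with about 130.

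**Expected records in the window** = yearly volume × 6/12, and **planned fraction** = planned ÷ expected:

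| Centre | Expected | Planned | Planned ÷ expected |
|---|---|---|---|
| Tertiary | 400/2 = 200 | 75 | 37.5% |
| Secondary | 250/2 = 125 | 45 | 36% |
| Primary | 12/2 = 6 | 8 to 10 | 133% to 167% |
| All | 331 | 128 to 130 | |

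Only the primary centre is out of line. For 8 to 10 records merely to exist in six months, its yearly volume would have to be 16 to 20 (8 × 2, 10 × 2) instead of 12.

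**Allowing for chance.** The number of admissions in a given half-year varies. If it is Poisson with mean 6 (an assumption; the protocol gives no distribution), then

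- P(at least 8) = 0.256, about 26%;
- P(at least 10) = 0.084, about 8%.

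In the half-years where 8 to 10 records do exist, taking 8 to 10 of them leaves few or none unselected.

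**Size of the shortfall.** 8 − 6 = 2, and 2/128 = 1.6% of the total. 10 − 6 = 4, and 4/130 = 3.1%. The total becomes 75 + 45 + 6 = 126.

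**Effect on the primary-centre description.** One patient moves a proportion by 1/6 = 16.7 points with 6 records, against 1/8 = 12.5 or 1/10 = 10 points with the planned number.

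**The case against.** The volumes and the planned counts are both given as approximate, and the gap may be as small as two records. Under the Poisson assumption a window with at least 8 records is not rare. In practice the archivist would probably hand over every record found, and section 5 ties collection to the availability of records. Precision at the primary centre is poor with 6 records and with 10, and no separate regression is planned there. All of this stands, and it is why the point is minor. It does not remove the contradiction: the planned count exceeds what the section's own figures lead one to expect, and the remark on availability is not a rule for a shortfall.

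A reader might infer two stronger conclusions, and the documents support neither.

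- *The total of 130 cannot be reached.* It can: the three windows are expected to hold about 331 records.
- *The power statement is wrong.* The protocol says that "A power calculation in G*Power on analyses of group averages indicates this sample size is largely sufficient to have a power of 95" per cent, with "an alpha set at 0.05 and a minimal effect size of 0.5". It names neither the test nor the effect metric. If 0.5 is Cohen's f in a three-group comparison, power is about 99.9% at 130 records and also at 126, so the claim holds with room to spare. If 0.5 is a two-group Cohen's d, two-sided power is about 75% for 75 v 45 and 81% for 65 v 65, and the claim fails. The text does not settle which is meant, so the 95% is not shown to be wrong. The unnamed test and metric are missing detail that a statistical analysis plan may supply. Nor does the protocol apply the 95% to comparisons of patient characteristics within the section 3.5 regressions.

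**Conclusion.** The concern holds for the primary-centre count, as a minor error. On section 3.3.2's own volumes about 6 primary-centre records are expected where 8 to 10 are planned, a shortfall of 2 to 4. On those volumes the centre would be a census, not the random sample that sections 3.3.1, 3.4 and 5 describe.

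The expected count rests only on admissions being spread evenly over the year. The 26% and 8% probabilities rest in addition on the Poisson assumption. The pooled analyses are not materially affected. The consequence is confined to the primary-centre description and to the instruction given to its archivist. No finding is made against the power statement.

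**What to change.** In section 3.3.2, replace the primary-centre figure of 8 to 10 with all eligible records in the six-month window (about 6). In sections 3.3.1, 3.4 and 5, say that the primary centre is a census of the window and that the other two centres are randomly sampled.

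Then choose one of two ways to settle the total:

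- state it as about 126 (75 + 45 + 6) in the synopsis, section 3.3.2 and section 5; or
- keep about 130 by drawing about four more records from the two larger centres, for example 77 + 47 + 6 = 130. That is 77/200 = 38.5% and 47/125 = 37.6% of their expected windows, so the sampling fractions there barely change.

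The cost is a few lines of text, plus either a slightly smaller stated sample or about four more chart reviews. The six-month window and the planned analyses stay as they are.
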